The median overall survival for patients treated with CPX-351 in the study was 9.56 months compared to 5.95 months for patients receiving 7+3, representing a 3.61 month improvement in favor of CPX-351. The hazard ratio (HR) was 0.69 (p=0.005) which represents a 31% reduction in the risk of death versus 7+3. The percentage of patients alive 12 months after randomization was 41.5% on the VYXEOS arm compared to 27.6% on the 7+3 arm. The percentage of patients alive 24 months after randomization was 31.1% on the CPX-351 arm compared to 12.3% on the 7+3 arm.

Event-free survival was also statistically significant in favor of CPX-351. The HR was 0.74 (p-value=0.021). The median event-free survival was 2.53 months in the CPX-351 arm compared to 1.31 months in the 7+3 arm.

CPX-351 also demonstrated a statistically significant improvement in induction response rate (CR+CRi of 47.7% versus 33.3%; p=0.016) and this significance was maintained for the analysis of CR alone (CR of 37.3% versus 25.6%, p=0.040).

Thirty-four percent of CPX-351 treated patients received a stem cell transplant (SCT) compared to 25% of 7+3 treated patients. In a landmark survival analysis of patients receiving a SCT, CPX-351 patients had significantly improved survival post-transplant (HR was 0.46 (p-value=0.0046)). The median overall survival had not been reached in the CPX-351 treated patients compared to 10.25 months in the 7+3 treated patients.

Thirty-day and sixty-day all-cause mortality favored CPX-351. Thirty-day mortality was 5.9% compared to 10.6% and sixty-day mortality was 13.7% versus 21.2%.

Grade 3-5 non-hematologic and hematologic adverse events were similar between the VYXEOS and 7+3 arms.

On the basis of the phase 3 trial data, CPX 351 was approved by the FDA for treatment of older patients aged 60-75 with prior myeloid hematologic disease.

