## 7.3 Dose Reductions and Delays

It is the intention of the study to treat every patient at full dose. Dose delays or modifications will be recommended at the discretion of the treating physician and PI. Doses may be delayed due to toxicities (for example hypersensitivity reactions). Any doses missed or delayed due to toxicity may be administered as soon as the patient has recovered from the toxicity. Toxicities will be graded using the CTCAE Version 4.0. See APPENDIX 4: Common Terminology Criteria for Adverse Events V4.0 (CTCAE)). Toxicities for cytarabine and daunorubicin are relatively well known, and are outlined in the product information for each of these drugs. Furthermore, dose reductions or protocol closure will be considered:

- 1) If >2 of the first 5 patients or >3 of the first 15 patients experience grade 4 toxicities, accrual will stop, the protocol reviewed, and dose modifications considered. If the incidence of grade 4 toxicity exceeds 20% of patients at any point after the first 15 patients have been treated, accrual will stop, the protocol will be reviewed, and dose modifications considered.
  
- 2) If 30-day mortality exceeds 20% (>3 of the initial 15 patients), *all further accrual will stop*. Subsequent enrollment after the first 15 subjects should ideally resume after the safety analysis is complete, however recognizing the acute nature of AML, it might not be possible to deny treatment to subjects in screening for ethical reasons sufficiently long to evaluate safety or efficacy. In other words, if the 30-day mortality for the preceding patients is less than 20%, study accrual will continue during the DSMB's safety analysis.

In the event that more than 15 subjects have enrolled before the safety analysis, only the first 15 subjects dosed will be informative for determining need for dose reduction as outlined in section 4.2.

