## **11 Statistical Considerations**

The primary objective of this non-randomized open label study is to evaluate the safety and efficacy of CPX-351 as a treatment for AML in elderly ( $\geq 60$  years of age) patients. Dose reductions or protocol closure will be considered:

- 1) If  $>2$  of the first 5 patients or  $>3$  of the first 15 patients experience grade 4 toxicities, accrual will stop, the protocol reviewed, and dose modifications considered. If the incidence of grade 4 toxicity exceeds 20% of patients at any point after the first 15 patients have been treated, accrual will stop, the protocol will be reviewed, and dose modifications considered.
- 2) If 30-day mortality exceeds 20% ( $>3$  of the initial 15 patients), *all further accrual will stop*. Subsequent enrollment after the first 15 subjects should ideally resume after the safety analysis is complete, however recognizing the acute nature of AML,

it might not be possible to deny treatment to subjects in screening for ethical reasons sufficiently long to evaluate safety or efficacy. In other words, if the 30-day mortality for the preceding patients is less than 20%, study accrual will continue during the DSMB's safety analysis.

In the event that more than 15 subjects have enrolled before the safety analysis, only the first 15 subjects dosed will be informative for determining need for dose reduction as outlined above.

Patients who die within the first 7 days because of leukemia related toxicity will be replaced. Those patients will be included in the analysis given the intention to treat for 30 day mortality and overall survival.

Analyses will primarily be descriptive in nature. Categorical variables will be summarized as frequency counts with associated percentages and continuous variables will be summarized as mean, standard deviation, median and range. Exact confidence intervals will be computed using the Clopper-Pearson method.

All analyses will be performed using SAS version 9.2 or higher.

Additional details regarding statistical analyses may be presented in a Statistical Analysis Plan (SAP).

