### **11.6 Safety Analysis**

Safety data will be analyzed and reported for all patients who receive at least one dose of study drug. Safety data summarized will include hematology, chemistries, vital signs,

adverse events (AEs) and physical examinations. Safety data will be summarized using descriptive statistics.

The number and proportion of patients with reported AEs and SAEs will be summarized by maximum grade. AEs that are related to study drug will be summarized in a separate table.

Laboratory values will be summarized both by actual result and by CTC toxicity grade (for selected laboratory parameters). Summaries of laboratory results at each scheduled time point will reflect the observed value at that time point as well as change from baseline. For selected laboratory parameters, the maximum grade for each patient will be summarized for each type of toxicity; a shift table will reflect baseline toxicity grade versus maximum observed on-treatment toxicity grade.

Vital signs and physical exam data will be summarized at each scheduled time point.

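### The toxicity stopping rule names grade 4 only, so a toxicity recorded solely as grade 5 is not counted, and after Day 30 or in patients 16-30 the mortality rule gives no clear trigger either

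*Combined protocol and SAP*

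**What the plan says.** Sections 7.3 and 11 carry the same two numbered rules.

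- **Item 1, toxicity.** The trigger is more than 2 of the first 5 patients with grade 4 toxicity, or more than 3 "of the first 15 patients experience grade 4 toxicities, accrual will stop, the protocol reviewed", and dose changes are considered. A third clause follows: "If the incidence of grade 4 toxicity exceeds 20% of patients at any point after the first 15 patients have been treated". Section 11 repeats it ("If the incidence of grade 4 toxicity exceeds 20% of patients at any point"). No clause adds *or higher* or *or 5*.
- **Item 2, mortality.** "If 30-day mortality exceeds 20% (>3 of the initial 15 patients"), all further accrual stops. Both sections then address over-enrolment before the safety analysis; 7.3 says that "only the first 15 subjects dosed will be informative for determining need for dose reduction as outlined in section 4.2".

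Toxicities are graded by CTCAE version 4.0 (7.3). Section 9.2.2 labels death as grade 5, and 9.2.4 sets fatal (grade 5) apart from life-threatening (grade 4) events. Where the protocol wants a range it writes one: grades 3-5 in the synopsis safety variables, and grade 3 or higher in 5.2 and 9.2.4. Mortality is assessed at Days 30 and 60 (synopsis; 11.4), but no boundary is attached to Day 60.

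**The concern.** A rule meant to halt accrual for severe toxicity should count the most severe grade. Read as written, this one does not name it. A death attributed to toxicity, with no grade 4 event recorded beforehand, adds nothing to item 1. It reaches item 2 only if it occurs by Day 30, and the stated boundary there concerns the initial 15 patients.

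Toxic deaths outside that window are foreseeable from the protocol itself. Neutrophil recovery usually takes 5-7 weeks (2.4), a second induction may be given up to 60 days after the first (4.4), and consolidation starts no earlier than 35 days after the last induction course (8.4). At stake is whether accrual, in a 30-patient trial of older adults, can continue past a level of life-threatening and fatal toxicity at which a reader would expect the rule to act.

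**Working it through.** **1. The plan's own boundary.** 3/15 = 20.0% and 4/15 = 26.7%, so more than 3 of 15 is the first count above 20%. The stated figure reproduces.

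**2. Which rule counts which patient, read literally.**

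| Patient | Item 1 (grade 4) | Item 2 (30-day deaths, initial 15) |
|---|---|---|
| Grade 4 event, survives | counted | not counted |
| Grade 4 event, later dies of toxicity | counted | only if by Day 30 and in initial 15 |
| Grade 5 only, by Day 30, initial 15 | not counted | counted |
| Grade 5 only, by Day 30, patients 16-30 | not counted | no clear trigger |
| Grade 5 only, after Day 30 | not counted | not counted |

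The last two rows are the gap. For example, suppose 4 of 15 patients have toxicity recorded only as grade 5 after Day 30, and nobody else has a grade 4 event. The counts are 0/15 and 0/15, and accrual continues. With grade 5 included, the count is 4/15 = 26.7% and accrual stops.

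The tallies also do not add. Three patients with grade 4 events plus three others with grade-5-only deaths by Day 30 make 6/15 = 40%, and neither rule fires.

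**3. How late deaths may fall.** Section 2.4 reports for the Phase 3 trial: "Thirty-day mortality was 5.9% compared to 10.6% and sixty-day mortality was 13.7% versus 21.2" per cent, CPX-351 first. The share of CPX-351 deaths by Day 60 that came after Day 30 is (13.7 − 5.9)/13.7 = 57%, leaving 43% by Day 30. These are deaths from all causes, not toxic deaths alone.

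**4. Illustrative size at 15 patients.** The documents give no grade 4 or toxic-death rate for this population, so all of these are assumptions:

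- *g* = 15% have a non-fatal grade 4 toxicity; *f* = 15% have a fatal toxicity.
- A share *s* of fatal cases has an earlier recorded grade 4 event.
- A share *e* of fatal cases dies by Day 30: either all, or 43% from step 3.
- Deaths from other causes and the first-5 clause are left out.

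Under the current rules, A (patients with any grade 4 event) has rate *g + sf*, and D (toxic deaths by Day 30) has rate *ef*. Accrual stops if A > 3 or D > 3, computed exactly from the multinomial with n = 15. Under the fix, the count has rate *g + f* = 30%. D is a subset of that count, so the probability is P(Bin(15, 0.30) > 3) = 0.703.

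| Share *s* with earlier grade 4 | Current, all deaths by Day 30 | Current, 43% by Day 30 | With fix |
|---|---|---|---|
| 0 | 34% | 19% | 70% |
| 0.5 | 51% | 45% | 70% |
| 0.8 | 63% | 61% | 70% |
| 1.0 | 70% | 70% | 70% |

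At lower assumed rates of 10% and 10% with *s* = 0, the current rules stop with probability 11% (6% with 43% of deaths by Day 30), against 35% with the fix.

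**5. The cost in extra stops.** Take a combined rate of exactly 20%, made up of 15% grade 4 and 5% fatal with no overlap. The fix gives P(Bin(15, 0.20) > 3) = 35%. The current wording gives P(Bin(15, 0.15) > 3) = 18%, and adding item 2 does not change the rounded figure.

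**The case against.** The strongest reply is that item 1 counts patients who experience grade 4 toxicity and sets no time limit. Someone who has a grade 4 event and later dies of it has experienced one and counts, whenever the death occurs. This stands, and it confines the gap to toxicities recorded solely as grade 5.

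Three stronger readings are tempting, and the documents do not support them.

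- A reader might infer from 11.6, "The number and proportion of patients with reported AEs and SAEs will be summarized by maximum grade", that every fatal case drops out of the grade 4 count. That sentence governs descriptive tables, not the stopping rule.
- A reader might take 34% (or 19%) against 70% as the effect. That is the extreme in which no fatal case had an earlier grade 4 event, and the difference shrinks to nothing as *s* approaches 1. The 15% fatal rate is also assumed, and it exceeds the 13.7% all-cause 60-day mortality for CPX-351 in the Phase 3 trial.
- A reader might say that the plan's 20% limit on grade 4 and 5 toxicity combined is breached. The plan sets two separate 20% limits and none on their sum.

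Two further points have some force. Item 1 does not say whether expected cytopenias count. If they do, most patients who die of toxicity may already be counted, and the rule may fire early regardless. That is a separate ambiguity; the narrower item 1 is eventually made, the more the missing grade 5 matters. Also, fatal events are not unmonitored: SAEs are reported promptly (9.2.4), and the DSMB reviews cumulative data semiannually and may convene as needed (11.7). That softens the consequence but supplies no numeric boundary for these deaths.

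**Conclusion.** The point holds in limited form. Item 1 in 7.3 and 11 omits toxicities recorded only as grade 5. When such a death falls after Day 30, or in patients 16-30, item 2 offers no clear numeric trigger. This rests on the text alone: the protocol separates grade 5 from grade 4 and writes ranges where it means them, so *grade 4* cannot safely be read as including death.

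The size is uncertain. It depends mainly on how often a fatal toxicity is preceded by a recorded grade 4 event, which the documents do not tell us. At the assumed 15% and 15% rates, the loss in stopping probability at 15 patients runs from 51 points (70 − 19) to zero; when half of fatal cases have an earlier grade 4 event it is 19 to 25 points (70 − 51, 70 − 45). A stopping rule should not depend on whether a grade 4 entry happened to be made before a death. The correction is worth making, but the finding does not show that fatal toxicity in general goes uncounted.

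**What to change.** In item 1 of both 7.3 and 11, replace *grade 4* with *grade 4 or 5* in each of the three clauses (first 5, first 15, and above 20% thereafter). Leave the thresholds as they are and keep the separate 30-day mortality rule. The change applies to whatever event types item 1 is taken to cover, and the two sections must be amended together so that they stay identical.

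The drafting cost is a few words. The operating cost is more frequent halts and reviews: in the 20% combined case above, 35% rather than 18% at 15 patients. The team should accept that figure knowingly.

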## 7.4 Concomitant Therapy

### 7.4.1 Premedication

#### 7.4.1.1 CPX-351

##### Nausea and vomiting:

Patients may be premedicated for nausea and vomiting according to institutional standards.

##### Hypersensitivity/Infusion-related reactions:

Patients will not be routinely premedicated for hypersensitivity or infusion-related reactions initially during the first infusion of the first treatment course. If the patient develops a hypersensitivity reaction then he/she should be pre-medicated at all subsequent infusions.

Suggested guidelines for management of hypersensitivity reactions:

##### **Mild symptoms (e.g., mild flushing, rash, pruritus):**

Stop infusion and supervise at bedside with monitoring of vital signs  
Reinitiate infusion slowly (halving the rate of infusion) +/- premedication

##### **Moderate symptoms (e.g. moderate rash, flushing, mild dyspnea, chest discomfort):**

Stop infusion and give IV diphenhydramine, 20-25 mg (or equivalent) and IV dexamethasone 10 mg.

Do not reinitiate infusion. Premedicate on re-treatment. Retreat at same dose and rate.

##### **Severe/life-threatening symptoms (e.g. hypotension requiring vasopressor therapy, angioedema, respiratory distress requiring bronchodilation therapy, generalized urticaria):**

Stop infusion. Administer IV diphenhydramine and dexamethasone as indicated above. Add epinephrine (adrenaline) or bronchodilators if indicated. Do not reinitiate infusion. Do not retreat. Report as a serious adverse event.

If hypersensitivity or infusion-related reactions become a clinically relevant toxicity, then premedication for hypersensitivity reactions will be instituted with drugs, doses and schedule according to each investigator's preference. Additionally, a decision may be made to prolong the infusion time to two hours or more.

##### Permitted therapy

Patients may receive ongoing supportive and palliative care (e.g. pain control) as clinically indicated throughout the study.

**Infection Prophylaxis:** Prophylactic use of antibiotics, antifungals, and antiviral drugs is highly recommended during the period of profound neutropenia until ANC returns to 500/ $\mu$ L or greater. The choice of medications will be according to institutional protocol. Use of anti-infective agents as prophylaxis and treatment must be documented on the case report forms.

**Growth Factor support:** The use of growth factors will be according to institutional protocol and according to ASCO criteria. Use of growth factors must be documented on the case report forms.

**Transfusion support:** The use of transfusion support (RBCs and platelets) will be according to institutional protocol. Use of transfusion support must be documented on the case report forms.

#### *7.4.2 Therapy that is not permitted*

Other anti-cancer treatment and other investigational therapy(ies) are not permitted during the Treatment Phase. In the event of persistent disease or relapse the patient may receive other anti-leukemic therapies and is followed for survival.

### **7.5 Duration of Protocol Treatment**

Patients may continue on study provided they have not met the criteria for discontinuation of therapy (See Section 5.2). Patients may receive up to 2 induction courses followed by up to 2 consolidation courses. After the Treatment Phase, patients will be followed for up to 5 years.

## **8 Assessment of Efficacy**

### **8.1 Efficacy Population**

All registered patients are evaluable for efficacy. Patients that die on or before Day 7 will be replaced.

### **8.2 Overall Survival**

Overall survival is measured from the date of registration to death from any cause. Patients not known to have died will be censored on the date they were last known to be alive. Patients will be followed for up to 5 years.

### **8.3 Event-free Survival**

Event-free survival is defined as the time from study registration to the date of induction treatment failure (persistent disease), progressive disease (PD) or death from any cause, whichever comes first. Patients alive and not known to have any of these events will be censored on the date of their last tumor assessment.

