PD	Persistent Disease
PhEur	European Pharmacopoeia
PHI	Protected Health Information
PK	Pharmacokinetics
PS	Performance Status
q.s.	quantum sufficiat
RBC	Red blood cells
SAE	Serious Adverse Event
SD	Standard deviation
sAML	Secondary AML
$T_{1/2}$	Half-life
t-AML	Therapy-related AML
Tmax	Time of occurrence of Cmax

u	Units
$\mu$ L	Microliter
ULN	Upper Limits of Normal
USP	United States Pharmacopeia
V	Volume
WHO	World Health Organization

---

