#### 4.6 Follow-up Phase

Patients will be followed at monthly intervals or more frequently depending on clinical circumstances until start of the next salvage treatment, death or for 1 year from date of enrollment. Patients alive and in remission after 1 year will be followed annually or more frequently depending on clinical circumstances for up to 5 years from enrollment. For EFS evaluation, events include: documentation of persistent AML after induction, relapse after achievement of CR/CRp/ CRi, or death. Bone marrow assessments will be performed at any time during follow up when recurrent cytopenias raise the suspicion of AML relapse. After documentation of persistent leukemia or relapse, follow-up for OS will continue. At the start of HSCT or non-protocol AML treatment of any sort or 30-days following the last dose, whichever occurs first, AE data collection will stop.

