## 5.2 Withdrawal of Patients

Patients will be discontinued from the Treatment Phase and enter the Follow-up Phase for assessment of efficacy endpoints under the following circumstances:

- Completion of Treatment Phase
- Persistent disease: lack of a response to treatment
- Relapsed disease: re-appearance of disease following CR, CRp, or CRI
- Unacceptable toxicity
- Patient non-compliance with protocol
- Administration of non-protocol chemotherapy
- Concurrent illness which, in the judgment of the investigator, effects assessment of clinical status to a significant degree, and requires discontinuation of protocol therapy.

Any adverse event that, in the judgement of the investigator, may cause severe or permanent harm if the study intervention is continued will result in subject discontinuation from the study. Any treatment related grade 3 or higher non-hematological toxicity that does not resolve to grade 2 within 14 days of receiving treatment for the event will result in subject discontinuation from the study.

During any phase of the study, if a patient requests to stop treatment and/or follow-up, the patient will be discontinued and no further information will be collected. The patient will be classified as withdrawal of consent.

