## 6.2 Evaluation during Treatment Phase

Inductions and consolidations are administered as courses. A course consists of the administration of therapy with scheduled assessments to evaluate the response to treatment. The first induction may end before the completion of all evaluations if a second induction is necessary, (see Section 4.4). Induction is completed when a patient has

- A confirmed CR (see section 8.4)
- A CRp or CRi (see section 8.4) and is to begin consolidation treatment before hematologic count recovery
- Persistent/recurrent disease (PD/relapse)
- Response evaluation cannot be performed because of the patient's condition and no further study treatment can or will be administered.

Patients with a CR or CRi may receive up to 2 consolidation treatments.

Procedure	Evaluation	Timing
Physical Exam	Objective review of body systems Weight BSA	Days 14 and 42
Vital Signs	Heart rate Blood pressure Temperature Respiratory rate	Days 14 and 42
Hematology	Hemoglobin White Blood Count Platelets Differential Count	Days 1, 3, 5, 7±3, 10±1, 14±2, then weekly (±2days) until whichever occurs last: - Day 42 - peripheral blood count recovery - removed from Treatment Phase

Procedure	Evaluation	Timing
Biochemistry	BUN Creatinine Uric Acid Electrolytes (Sodium, Potassium, Chloride) Bilirubin Alkaline phosphatase AST or ALT LDH Protein Calcium Albumin Glucose	Days 1, 3, 5, 7±3, 10±1, 14±2, then weekly (±2days) until whichever occurs last: - Day 42 - peripheral blood count recovery - removed from Treatment Phase
Bone Marrow Evaluation	Morphology	As needed to confirm response or determine antileukemic effect and need for second induction.
Cytogenetics Molecular Studies	Cytogenetics Molecular Studies	Required in patients with a CR, CRp, or CRI with positive baseline findings (perform at the time of bone marrow assessment for CR or CRI). Optional in patients with normal baseline cytogenetics/molecular studies.
Diagnostic Imaging	Echocardiography, MUGA or cardiac MRI scan	After the last induction and before each consolidation cycle.
Questionnaires	MOCA, Blessed, FACT-Leu	Days 7±3, 42±3, Induction 2 Day 1(±3)
Adverse Events/Toxicity	CTCAE v.4 assessment	Continual assessment starting from the first dose until 30 days after completion of the Treatment Period.
Concomitant Medications		Continual assessment during Treatment Period.

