## 8.4 Response Assessment Criteria

During the Treatment Phase patients will be assessed for response according to the following criteria:

Complete remission (CR) a	Bone marrow blasts <5%; absence of blasts with Auer rods; absence of extramedullary disease; absolute neutrophil count $\geq 1.0 \times 10^9/L$ (1000/ $\mu$ L); platelet count $\geq 100 \times 10^9/L$ (100,000/ $\mu$ L); independence from red cell transfusions
CR with incomplete recovery (CRI) b	All CR criteria except for residual neutropenia ( $< 1.0 \times 10^9/L$ [1000/ $\mu$ L]) or thrombocytopenia ( $< 100 \times 10^9/L$ [100,000/ $\mu$ L])
Best Response	See Section 8.4.1
Treatment failure	
Persistent Disease (PD)	Failure to achieve CR or CRI; only includes patients surviving $\geq 7$ days following completion of initial treatment, with evidence of persistent leukemia (blasts in peripheral blood, extramedullary leukemia, or persistence in the bone marrow)
Death in aplasia	Deaths occurring $\geq 7$ days following completion of initial treatment while cytopenic; with an aplastic or hypoplastic bone marrow obtained within 7 days of death, without evidence of persistent leukemia
Death from indeterminate cause	Deaths occurring before completion of therapy, or $< 7$ days following its completion; or deaths occurring $\geq 7$ days following completion of initial therapy with no blasts in the blood, but no bone marrow examination available at recovery
Relapse c	Bone marrow blasts $\geq 5\%$ ; or reappearance of blasts in the blood after achievement of a CR or CRI; or development of extramedullary disease

aBone marrow assessment REQUIRED to confirm CR. All criteria need to be fulfilled; marrow evaluation should be based on a count of 200 nucleated cells in an aspirate with spicules; if ambiguous, consider repeat exam after 5 to 7 days; flow cytometric evaluation may help to distinguish between persistent leukemia and regenerating normal marrow; a marrow biopsy should be performed in cases of dry tap, or if no spicules are obtained; no minimum duration of response required.

bBone marrow assessment REQUIRED to confirm CRI. Some patients may not achieve complete hematologic recovery prior to initiation of consolidation. CRI cannot be declared earlier than Day 35 to allow adequate time for documentation of peripheral blood recovery. Consolidation may begin no earlier than 35 days after the last induction course.

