### *11.1.2 Secondary Endpoints*

Secondary efficacy endpoints include complete response (CR, CRp, CRI, and CR+CRp+CRI), the relationship of cognitive function to treatment response and OS, event-free survival and morphologic leukemia free state (as defined in Section 8). Secondary safety endpoints include incidence of AEs and SAEs, laboratory measurements (hematology and biochemistry), vital signs and physical examinations.

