### **11.5 Analysis of Secondary Endpoints**

Time dependent endpoints, such as remission duration (relapse-free survival) and event-free survival (EFS), will be evaluated using Kaplan-Meier methods; estimates of event rates will be computed and a survival curve generated.

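### Section 8.3 lists progressive disease, a term without criteria, where 4.6 lists relapse as an EFS event, and 8.3 and 8.5 censor at an undefined last tumor assessment

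*Combined protocol and SAP*

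**What the plan says.** **EFS events.** Section 11.1.2 lists "event-free survival and morphologic leukemia free state (as defined in Section 8") among the secondary endpoints, so Section 8 supplies the definition. Section 8.3 runs EFS from registration to "induction treatment failure (persistent disease), progressive disease (PD) or death from any cause, whichever comes first". Section 4.6 gives its own list for EFS evaluation: "events include: documentation of persistent AML after induction, relapse after achievement of" CR, CRp or CRi, or death.

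**Meaning of PD.** The abbreviation list expands PD as "Persistent Disease", and the response table in 8.4 uses it in the same sense. Section 6.2 ends induction at "Persistent/recurrent disease (PD/relapse"), pairing PD with persistent disease and relapse with recurrence. Section 5.2 has one withdrawal reason for persistent disease and another for relapse: "Relapsed disease: re-appearance of disease following CR, CRp, or CRI". Section 8.4 gives criteria for persistent disease and for relapse, and none for progressive disease.

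**Censoring and follow-up.** Sections 8.3 (EFS) and 8.5 (remission duration) censor patients without an event at the date of the last tumor assessment, a term that is not defined. Follow-up marrows are done on suspicion of relapse, not at fixed times (4.6, 6.4, Appendix 2). Monthly counts and status reports run to one year. After that, the relapse-status and hematology rows of 6.4 record only relapse and new therapies, the marrow row adds any marrows done, and the survival row records death or alive at Year 5. Appendix 2 marks a status report and hematology in its Years 2-5 column, and 4.6 plans at least annual follow-up of patients in remission.

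**Analysis.** Section 11.5 uses Kaplan-Meier methods for both endpoints: "estimates of event rates will be computed and a survival curve generated".

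**The concern.** Two sections give different EFS event lists. A programmer working literally from 8.3 has no criteria for its second item. If PD is read as the protocol expands it, that item repeats the first one and relapse drops out. A responder who relapses and is still alive then remains event-free until death, and EFS rates are overstated. Under 4.6 the same patient has an event at relapse.

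The undefined censoring date raises a separate problem. If relapse-free patients stop contributing follow-up around month 12 while relapses and deaths in years 2 to 5 still enter at their true dates, those who leave the risk set early are exactly those who do well. That is informative censoring, and it pulls the remission-duration curve down.

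In both cases the choice could be made after the data are seen, and relapse-free dates that were not recorded at the time may be hard to recover later.

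**Working it through.** The plan gives no figure for either endpoint to reproduce, so the event definition is a comparison of text and the sizes below are illustrative.

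**1. Event lists side by side**

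| Event | 8.3 | 4.6 | Criteria in 8.4 |
|---|---|---|---|
| Persistent disease after induction | yes | yes | yes |
| Progressive disease | yes | no | none |
| Relapse after remission | not named | yes | yes (names CR and CRi only) |
| Death | yes | yes | not needed |

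**2. Size of the event difference**

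Input from the documents: response rate 47.7% (CR+CRi, phase 3 trial in 2.4).

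Assumed: median time to relapse 8 months in those who relapse; median survival after relapse 5 months; death in remission 1% per month; remission at day 35-56 (midpoint about 1.5 months); all non-responders have an event by day 60; 0% or 30% of responders never relapse.

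Monthly hazards:
- relapse λ = ln 2/8 = 0.0866
- death after relapse μ = ln 2/5 = 0.1386
- leaving remission a = 0.0866 + 0.01 = 0.0966

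Time in or after remission at month 12: t = 12 − 1.5 = 10.5 months.

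- Relapsed and alive at t, among those who can relapse: λ/(μ − a) × (e^(−at) − e^(−μt)) = 0.267.
- Gap in 12-month EFS, 0% never relapsing: 0.477 × 0.267 = 12.7 points, or 30 × 0.127 = 3.8 patients.
- Gap, 30% never relapsing: 0.477 × 0.7 × 0.267 = 8.9 points, or 2.7 patients.
- EFS with relapse counted, 0%: 0.477 × 0.3625 = 17.3%. Relapse omitted: 17.3 + 12.7 = 30.0%.
- EFS with relapse counted, 30%: 0.477 × (0.7 × 0.3625 + 0.3 × e^(−0.105)) = 25.0%. Relapse omitted: 25.0 + 8.9 = 33.9%.

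A simulation of 400,000 patients per scenario agrees: 17.2 vs 30.0%, and 25.0 vs 33.9%. Median EFS moves only from 1.86-1.87 to 1.90 months, because most events are induction failures. With relapse medians of 6-12 months, post-relapse medians of 3-8 months and 0-30% never relapsing, the 12-month gap is 4.8 to 19.2 points.

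**3. Size of the censoring effect on remission duration**

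Same assumptions, with 36-60 months of follow-up from registration, or 34.5-58.5 months from remission. Let S(u) be the true proportion in remission u months after remission, and c the proportion still in remission at end of follow-up. If all of c is censored at month 12 and everyone else's event is counted, the 24-month Kaplan-Meier value is S(10.5) × [S(24) − c]/[S(10.5) − c].

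| Never relapsing | S(10.5) | S(24), true | c | Censored at month 12 |
|---|---|---|---|---|
| 0% | 0.362 | 9.8% | 0.014 | 8.8% |
| 30% | 0.524 | 30.5% | 0.199 | 17.1% |

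The bias is about 1 point if everyone relapses, because almost no one is left to be censored. It is about 13 points if 30% never relapse. When remitters are censored at their last annual contact, the simulation returns the true values (9.7% and 30.5%).

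**4. Sampling error for scale**

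Exact 95% interval for 8/30: 12-46%. About 0.477 × 30 = 14 responders are expected; for 4/14 the interval is 8-58%.

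**The case against.** The strongest reply is that the protocol has one sensible EFS event set and one badly chosen label. Section 8.3 lists progressive disease apart from persistent disease, so something further was meant. Section 4.6 says what it is, 8.4 gives criteria for it, and 8.5 counts it. This largely stands: relapse was very probably intended, and the 9-13 point gap measures an unlikely literal reading, not an expected error. It does not remove the contradiction, because 11.1.2 sends the analyst to Section 8 and not to 4.6.

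On censoring, 4.6 and Appendix 2 already plan later contacts, the marrow row of 6.4 keeps any later marrows, and 8.4 accepts blood blasts as relapse, so counts may well qualify as an assessment. That also stands. The bias needs 6.4 to be followed alone, and its larger values need an assumed share of responders who never relapse.

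A reader might infer that remitters will be censored back at their remission marrow. The documents do not support that as the plan's rule: nothing restricts the assessment to a marrow, and further marrows are foreseen when CRp or CRi is upgraded (8.4.1) and when counts fall (Appendix 2).

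The model is also not calibrated. It gives a median EFS of about 1.9 months, against 2.53 months for CPX-351 in 2.4.

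**Conclusion.** The point holds at minor-to-moderate severity. Sections 8.3 and 4.6 contradict each other on an operative endpoint rule and can give different EFS from the same data. The literal reading of 8.3 overstates EFS rates and hardly changes the median. The censoring term is undefined, and 6.4 taken alone requires no dated relapse-free contact between month 12 and Year 5. That can bias remission duration downward by an amount that depends on the unknown share who never relapse: about 1 point at 24 months if all relapse, larger otherwise, and about zero if the contacts in 4.6 and Appendix 2 are dated and used.

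Every size here rests on the stated assumptions; only the response rate comes from the documents. Sampling error with 30 patients is larger than either effect. A reader might go on to conclude that the trial's main findings are at risk. They are not: EFS and remission duration are secondary and descriptive, and overall survival has its own clear censoring rule in 8.2. Overall survival, its power, 30-day mortality and the stopping rules do not depend on this wording.

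**What to change.** 1. In 8.3, replace *progressive disease (PD)* with relapse after CR, CRp or CRi, matching 4.6. Make the relapse row of 8.4 name CRp as well as CR and CRi, so that the criteria cover every responder.
2. In 8.3 and 8.5, censor at the last date on which the patient was documented alive and relapse-free, by any evaluation against 8.4 (marrow or blood count) or by a dated status report.
3. Reconcile 6.4 with Appendix 2 and 4.6 so that the date of each relapse-free contact in years 2 to 5 is recorded.

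The first two changes are wording only. The third adds at most one date per contact; if Appendix 2 and 4.6 already govern, the contacts themselves are planned. The downside is that relapse-free status then rests partly on counts or clinical status and not on a marrow.
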